3.1.4. Safety Analysis Set

The Safety Analysis Set includes all subjects who were randomized and received at least 1 dose of study drug. This is the primary analysis set for safety analyses.

3.1.5. Pharmacokinetic Analysis Set

The PK Analysis Set will include all subjects who (1) are randomized into the study, (2) have received at least 1 dose of active study drug, and (3) have at least 1 nonmissing PK concentration value for any analyte of interest reported by the PK lab. The PK analysis set will be used for general PK analyses.

CCI

[REDACTED]

[REDACTED]

[REDACTED]

[REDACTED]

3.2. Subject Grouping

For analyses based on the All Randomized Analysis Set or the FAS, subjects will be grouped according to the treatment group to which they were randomized. For all other analyses, subjects will be grouped according to the actual treatment received. The actual treatment received will differ from the randomized treatment only when their actual treatment differs from randomized treatment for the entire treatment duration.

Subjects will be grouped as follows for table summary:

- Treatment Group 1: SC LEN + (F/TAF → TAF)
- Treatment Group 2: SC LEN + (F/TAF → BIC)
- Treatment Group 3: Oral LEN + F/TAF
- Treatment Group 4: B/F/TAF
- Treatment Groups 1 and 2: SC LEN (for all tables unless specified otherwise)
- Treatment Groups 1, 2 and 3: LEN (for all tables unless specified otherwise)

3.3. Strata and Covariates

Randomization was stratified by HIV-1 RNA level ($\leq 100,000$ copies/mL or $> 100,000$ copies/mL) at screening.

Efficacy analyses will include HIV-1 RNA stratum ($\leq 100,000$ vs. $> 100,000$ copies/mL) at baseline as a stratification factor. The HIV-1 RNA stratum will be reclassified using baseline HIV-1 RNA level for analysis purposes.

3.4. Examination of Subject Subgroups

3.4.1. Subject Subgroups for Efficacy Analyses

The proportion of subjects with HIV-1 RNA < 50 copies/mL at Week 54 as determined by the United States (US) Food and Drug Administration (FDA)-defined snapshot algorithm {[U. S. Department of Health and Human Services 2015](#)} will be analyzed for the following subject subgroups based on FAS:

- Age (years): (a) < 50 and (b) ≥ 50
- Sex: (a) male and (b) female
- Race: (a) black and (b) nonblack
- Baseline HIV-1 RNA (copies/mL): (a) $\leq 100,000$ and (b) $> 100,000$
- Baseline CD4 Cell Count (/uL): (a) < 200 and (b) ≥ 200

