Baseline disease characteristics were similar across the treatment groups. Overall, the median (Q1, Q3) baseline HIV-1 RNA value was 4.37 (3.86, 4.74) \log_{10} copies/mL, and the median (Q1, Q3) baseline CD4 cell count was 437 (332, 599) cells/ μ L. Among the 182 participants, most had HIV-1 RNA \leq 100,000 copies/mL (85.2%, 155 participants) and a CD4 cell count range of \geq 350 to $<$ 500 cells/ μ L (31.9%, 58 participants) or \geq 500 cells/ μ L (37.4%, 68 participants).

Efficacy Results:

Primary Efficacy End Point

HIV-1 RNA $<$ 50 copies/mL at Week 54 Using the US FDA-Defined Snapshot Algorithm

The primary analysis at Week 54 demonstrated similar results in each treatment group, with no significant difference between each of the GS-6207-containing groups and the BVY group, as follows:

- GS-6207 total: 136 of 157 participants (86.6%)
- SC GS-6207 + (DVY \rightarrow TAF): 47 of 52 participants (90.4%)
- SC GS-6207 + (DVY \rightarrow BIC): 45 of 53 participants (84.9%)
- Oral GS-6207 + DVY: 44 of 52 participants (84.6%)
- BVY: 23 of 25 participants (92.0%)

For participants with HIV-1 RNA $<$ 50 copies/mL at Week 28, the proportion with HIV-1 RNA $<$ 50 copies/mL at Week 54 using the US FDA-defined snapshot algorithm were also similar in each treatment group, with no significant difference between each of the GS-6207-containing groups and the BVY group, as follows:

- GS-6207 total: 135 of 147 participants (91.8%)
- SC GS-6207 + (DVY \rightarrow TAF): 46 of 49 participants (93.9%)
- SC GS-6207 + (DVY \rightarrow BIC): 45 of 49 participants (91.8%)
- Oral GS-6207 + DVY: 44 of 49 participants (89.8%)
- BVY: 23 of 25 participants (92.0%)

Secondary Efficacy End Points

Week 28

Results from the secondary efficacy analysis of Week 28 data of Study GS-US-200-4334 demonstrated similar results in each treatment group, with no significant difference between each of the GS-6207-containing treatment groups and the BVY treatment group with respect to the proportion of participants with HIV-1 RNA < 50 copies/mL using the US FDA-defined snapshot algorithm, the change from baseline in log₁₀ HIV-1 RNA, and the change from baseline in CD4 cell count.

HIV-1 RNA < 50 copies/mL using the US FDA-defined snapshot algorithm

- GS-6207 total: 147 of 157 participants (93.6%)
- SC GS-6207 + (DVY → TAF): 49 of 52 participants (94.2%)
- SC GS-6207 + (DVY → BIC): 49 of 53 participants (92.5%)
- Oral GS-6207 + DVY: 49 of 52 participants (94.2%)

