4.2. Inclusion Criteria

Participants must meet all of the following inclusion criteria to be eligible for participation in this study:

- 1) Willing and able to provide written informed consent prior to performing study procedures
- 2) Aged ≥ 18 years
- 3) Antiretroviral naïve with no use of any ARV within one month of Screening. Use of pre-exposure prophylaxis (PrEP) (any duration), post-exposure prophylaxis (PEP) (any duration), or HIV-1 treatment (< 10 days therapy total) > 1 month prior to Screening is permitted
- 4) Plasma HIV-1 RNA ≥ 200 copies/mL at Screening
- 5) CD4+ cell count ≥ 200 cells/ μ L at Screening
- 6) A negative serum pregnancy test is required for all women at screening
- 7) Participants of childbearing potential who engage in heterosexual intercourse must agree to use protocol-specified method(s) of contraception as defined in [Appendix 4](#).
- 8) Lactating women must agree to discontinue nursing before the study drug(s) is administered

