6.2. Pretreatment Assessments

6.2.1. Screening Visit

Participants will be screened within 30 days before randomization to determine eligibility for participation in the study. The following will be performed and documented at screening:

- Obtain written informed consent
- Obtain demographic information, including gender at birth, sexual orientation, and gender identity
- Obtain medical history including HIV-1 disease-related events, available historical genotype/phenotype reports and prior medications within 30 days of the screening visit. Samples for genotype reports will be collected at screening but results are not required to determine eligibility.
- Complete physical examination (urogenital/anorectal exams will be performed at the discretion of the investigator) including, vital signs (blood pressure, pulse, respiration rate, and temperature, body weight, and height)
- 12-lead ECG performed supine
- Obtain blood and urine samples as noted in [Section 6.5](#)
- Record any SAEs and all AEs related to protocol-mandated procedures occurring after signing of the consent form.

Participants meeting all of the inclusion criteria and none of the exclusion criteria will return to the clinic within 30 days after screening for randomization into the study.

Participants not meeting one or more inclusion criteria and/or meeting one or more exclusion criteria may be rescreened on a case-by-case basis upon written approval from Gilead Medical Monitor or Study Director.

From the time of obtaining informed consent through the first administration of study drug, record all SAEs, as well as any AEs related to protocol-mandated procedures on the AEs electronic case report form (eCRF). All other untoward medical occurrences observed during the screening period, including exacerbation or changes in medical history are to be considered medical history. See Section 7 Adverse Events and Toxicity Management for additional details.

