3.8. Analysis Visit Windows

3.8.1. Definition of Key Dates and Study Day

Study Day 1 is defined as the day when the first dose of study drug was taken, as recorded on the Study Drug Administration eCRF. For subjects in Treatment Groups 1-3, the earliest of the first dose dates of any component (ie, LEN or F/TAF) is considered as the first dose date of the study drug.

Last Dose Date is defined as follows for subjects who prematurely discontinued study drug according to Study Drug Completion eCRF.

- For subjects who receive SC injection, the last dose date is defined as the latest nonmissing end date of the study drug used with LEN.
- For subjects who do not receive SC injection, the last dose date is defined as the earliest of the last dose date of any study drug.
- If the date of last dose is incomplete or missing (eg, due to lost to follow-up), the latest nonmissing study drug start dates and end dates, the clinic visit dates, and the laboratory visit dates excluding the dates of any follow-up visits will be used to impute the last dose date.

Study Days are calculated relative to Study Day 1 of study drug and derived as follows:

- For postdose study days: Assessment Date – First Dose Date + 1
- For days prior to the first dose: Assessment Date – First Dose Date

Baseline Value is defined as the last value obtained on or prior to the first dose of study drug.

Last Study Date is the latest nonmissing clinic visit dates, and/or the laboratory visit dates, and/or latest AE onset date and end date, whichever is latest, including the any follow-up visit dates, for subjects who prematurely discontinued study according to the Study Completion eCRF.

Last Exposure Date is defined as follows for subjects who prematurely discontinued study drug according to Study Drug Completion eCRF. This date is defined considering the prolonged exposure of LEN after the last dose date of LEN.

- Treatment Groups 1 and 2:
 - For subjects who receive SC injection, last exposure date is defined as last study date.
 - For subjects who do not receive SC injection, last exposure date is defined as the minimum of the last dose date plus 60 days and the last study date.

- Treatment Group 3: last exposure date is defined as the minimum of the last dose date plus 60 days and the last study date.
- Treatment Group 4: last exposure date is defined as the minimum of the last dose date plus 30 days and the last study date.

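### The CD4 subgroup is cut at 200 cells/µL in a trial that requires 200 or more at screening, so one row should be nearly empty and the other should nearly repeat the overall result

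*SAP*

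**What the plan says.** SAP 3.4.1 lists five subgroup factors for the primary endpoint in the Full Analysis Set. The last is "Baseline CD4 Cell Count (/uL): (a) < 200 and (b") 200 or more. SAP 6.4 makes these results descriptive, with exact 95% confidence intervals, and SAP 3.5 makes no adjustment for multiplicity.

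Protocol 4.2, criterion 5, requires "CD4+ cell count ≥ 200 cells"/µL at Screening, and SAP 1.2 repeats this. The two rules use different measurements. Protocol 6.2.1 says "Participants will be screened within 30 days before randomization to determine eligibility", whereas under SAP 3.8.1 the baseline value "is defined as the last value obtained on or prior to the first dose of study drug", which is normally the Day 1 sample.

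Protocol 1.2.2.8 summarises the 182 treated participants of this same trial: "baseline CD4 cell count was 437 (332, 599) cells"/µL (median and quartiles), with "31.9%, 58 participants" at 350 to below 500 and "37.4%, 68 participants" at 500 or above. The number below 200 is not given.

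SAP 5.2 tabulates baseline CD4 in five bands with boundaries at 50, 200, 350 and 500. The SAP gives no reason for using 200 in the subgroup, no minimum row size and no rule for merging sparse rows.

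**The concern.** A CD4 subgroup is there to show whether response differs between participants with lower and higher immune status. A cut at the entry threshold removes almost everyone from one side. The few who remain are also an odd group: they tested at 200 or above and then lower within about a month, so most will sit close to the threshold and were picked out partly by measurement variation. They do not represent people with an established low count.

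What is at stake is small. One of five planned subgroup factors for the primary endpoint would use table space without answering its question, although the trial has enough spread in CD4 to say something.

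**Working it through.** **1. Reported baseline figures.** 58/182 = 31.9% and 68/182 = 37.4%; both reproduce. Hence 182 − 58 − 68 = 56 (30.8%) were below 350 and 126 (69.2%) at or above it. How the 56 divide at 200 is not reported. A first quartile of 332 shows only that fewer than about a quarter of the 182 were below 200, so a narrower figure needs a model.

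**2. Shape of the distribution.** Log-normal fitted to the quartiles:
- log SD = (ln 599 − ln 332) / (2 × 0.6745) = 0.437
- share below 200, ignoring the entry rule = Φ((ln 200 − ln 437)/0.437) = 3.7%, or about 7 of 182

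A normal curve fitted to the same interquartile range, again ignoring the entry rule, would give about 21. It fits poorly: the upper quartile is 162 above the median and the lower only 105 below it, and a log-normal allows for that skew.

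**3. Imposing the entry rule.** Each simulated participant has a true log count and two independent readings, screening and baseline. The within-person SD is √ln(1 + CV²), and the total log SD is held at 0.437. Only those with screening at 200 or above are kept. The documents give no within-person CV, so a range is assumed.

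| Assumed CV | Share with baseline < 200 | Expected of 182 | Per 50 | Per 25 | Chance of none among 25 |
|---|---|---|---|---|---|
| 10% | 1.1% | 1.9 | 0.5 | 0.3 | 77% |
| 15% | 1.6% | 2.9 | 0.8 | 0.4 | 67% |
| 20% | 2.1% | 3.8 | 1.0 | 0.5 | 59% |
| 25% | 2.5% | 4.5 | 1.2 | 0.6 | 53% |
| 30% | 2.9% | 5.3 | 1.5 | 0.7 | 48% |

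The simulated baseline quartiles (333 to 338, 445 to 446, 594 to 595) lie close to the reported 332, 437 and 599. Eligibility deviations would add to these counts; the documents do not number them.

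**4. What the lower row would show.** Exact 95% intervals with every participant responding: 1/1 gives 2.5% to 100%, 2/2 gives 15.8% to 100%, 3/3 gives 29.2% to 100%.

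**5. What the upper row would show.** Protocol 1.2.2.8 reports "GS-6207 total: 136 of 157 participants (86.6"%). Taking out 3 participants gives 133/154 = 86.4% if all three responded, 134/154 = 87.0% if one failed, and 136/154 = 88.3% if all failed. For B/F/TAF (23/25 = 92.0%), taking out one gives 22/24 = 91.7% or 23/24 = 95.8%.

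**6. A split at 350.** Overall it is 56 v 126. CD4 by treatment group is not reported and randomization was stratified on HIV-1 RNA only, so the group figures assume an even spread:
- groups of 52: 52 × 56/182 = 16.0 v 36.0
- group of 53: 53 × 56/182 = 16.3 v 36.7
- B/F/TAF, 25: 25 × 56/182 = 7.7 v 17.3

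Precision stays modest: 14/16 responders gives an exact interval of 62% to 98%, and 7/8 gives 47% to 99.7%.

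**The case against.** A reader might infer that the SAP contradicts the eligibility criteria, or that the lower row must be empty. Neither follows. Eligibility rests on the screening count and the subgroup on a later one, and SAP 4.3 summarises participants enrolled outside the criteria, so the row can legitimately be populated. The threshold also has clinical standing: Protocol 1.2.2.7 calls a count below 200 a mark of severe immune suppression. That remark, however, concerns another study in which 75% of Cohort 1 were below 200, and it does not fill the row here.

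The analysis is descriptive in a trial that the SAP calls non-confirmatory, and nothing is decided on this row. Sparse rows occur elsewhere in the same list: with 93.4% male, about 12 of 182 are not. This limits the importance of the point. It does not explain a cut that the trial's own entry rule empties.

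The count below 200 is unreported, so the size of the row is a model result. That objection stands, and it is why a range is given.

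The choice of 350 is a judgement. The 500 boundary is also in SAP 5.2 and would split 114 v 68. The reason to prefer 350 is that it isolates the lower end of CD4 while leaving a usable number there.

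Finally, replacing the 200 cut now would put a post hoc subgroup in place of a prespecified one. That also stands, and the fix is an addition for this reason.

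**Conclusion.** The point holds as a minor one. On a log-normal shape and a within-person CV of 10% to 30%, about 2 to 5 of 182 participants are expected below 200 at baseline, and more likely than not none or one in B/F/TAF. The other row, about 97% to 99% of the Full Analysis Set, stays within about 2 points of the overall lenacapavir rate when 3 participants are removed. In B/F/TAF the near-repetition is looser, since one excluded failure would move the rate by 3.8 points.

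The direction follows from the entry rule and the reported quartiles; the exact size depends on the assumptions. It would go too far to say that the subgroup gives no information at all, since the few participants below 200 would at least be shown separately. Nor do the documents support any inference that the primary estimate, its interval or its interpretation is affected.

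**What to change.** Add a baseline CD4 subgroup of below 350 v 350 or more cells/µL, citing the boundary in SAP 5.2 as its source. Keep the planned 200 row and label it sparse, with its counts shown by treatment group.

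The Week 54 SAP was signed in October 2021 and the protocol already reports Week 54 results. The 350 cut should therefore be specified for the Week 80 analysis (SAP 2.1.3), or reported for Week 54 as an added exploratory table and documented in the clinical study report, as SAP 1 requires for changes after finalization. Stating that the cut comes from existing display categories, and not from outcomes by CD4, limits the concern about data-driven choice.

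The cost is one extra descriptive table, with no new data and no effect on participants. It will remain imprecise in B/F/TAF, where about 8 participants would fall below 350 if CD4 is evenly spread.

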3.4.2. Subject Subgroups for Safety Analyses

Incidence of all treatment-emergent AEs (TEAEs) will be analyzed for the following subject subgroups:

- Age (years): (a) < 50 and (b) ≥ 50
- Sex: (a) male and (b) female
- Race: (a) black and (b) nonblack

3.5. Multiple Comparisons

Adjustments for multiplicity will not be made in this Phase 2, non-confirmatory trial.

3.6. Missing Data and Outliers

3.6.1. Missing Data

In general, missing data will not be imputed unless methods for handling missing data are specified. Exceptions are presented in this document.

For missing last dose date of study drug, imputation rules are described in Section 3.8.1. The handling of missing or incomplete dates for AE onset is described in Section 7.1.5.2, and for prior and concomitant medications in Section 7.4.

3.6.2. Outliers

Outliers will be identified during the data management and data analysis process, but no sensitivity analyses will be conducted. All data will be included in the data analysis.

3.7. Data Handling Conventions and Transformations

Only year of birth is collected in this study. The following conventions will be used for the imputation of date of birth when it is partially missing or not collected:

- If only month and year of birth is collected, then “15” will be imputed as the day of birth
- If only year of birth is collected, then “01 July” will be imputed as the day and month of birth
- If year of birth is missing, then date of birth will not be imputed.

In general, age collected at Day 1 (in years) will be used for analyses and presented in listings. If age at Day 1 is not available for a subject, then age derived based on date of birth and the Day 1 visit date will be used instead. If an enrolled subject was not dosed with any study drug, the randomization date will be used instead of the Day 1 visit date. For screen failures, the date the first informed consent was signed will be used for the age derivation. Age required for longitudinal and temporal calculations and analyses (e.g., estimates of creatinine clearance, age at date of AE) will be based on age derived from date of birth and the date of the measurement or event, unless otherwise specified.

Non-PK data that are continuous in nature but are less than the lower limit of quantitation (LOQ) or above the upper LOQ will be imputed as follows:

- A value that is 1 unit less than the lower LOQ at the same precision level of the originally reported value will be used to calculate descriptive statistics if the datum is reported in the form of “< x” (where x is considered the lower LOQ). For example, if the values are reported as < 50 and < 5.0, values of 49 and 4.9, respectively, will be used to calculate summary statistics. An exception to this rule is any value reported as < 1 or < 0.1, etc. For values reported as < 1 or < 0.1, a value of 0.9 or 0.09, respectively, will be used to calculate summary statistics.
- A value that is 1 unit above the upper LOQ will be used to calculate descriptive statistics if the datum is reported in the form of “> x” (where x is considered the upper LOQ). Values with decimal points will follow the same logic as above.
- The lower or upper LOQ will be used to calculate descriptive statistics if the datum is reported in the form of “≤ x” or “≥ x” (where x is considered the lower or upper LOQ, respectively).

Sparse PK concentration values that are below the limit of quantitation (BLQ) will be presented as “BLQ” in the data listing.

Logarithmic (base 10) transformations will be applied to HIV-1 RNA data for efficacy analysis. HIV-1 RNA results of ‘No HIV-1 RNA detected’ and “<20 cp/mL HIV-1 RNA Detected” will be imputed as 19 copies/mL for analysis purposes.

Natural logarithm transformation will be used for analyzing concentrations and PK parameters in intensive PK samples. Concentration values that are BLQ will be presented as “BLQ” in the concentration data listing. Values that are BLQ will be treated as 0 at predose time points, and one-half the value of the LOQ at postdose time points for summary purposes.

The following conventions will be used for the presentation of summary and order statistics for intensive PK concentrations:

- If at least 1 subject has a concentration value of BLQ for the time point, the minimum value will be displayed as “BLQ.”
- If more than 25% of the subjects have a concentration data value of BLQ for a given time point, the minimum and Q1 values will be displayed as “BLQ.”
- If more than 50% of the subjects have a concentration data value of BLQ for a given time point, the minimum, Q1, and median values will be displayed as “BLQ.”
- If more than 75% of the subjects have a concentration data value of BLQ for a given time point, the minimum, Q1, median, and Q3 values will be displayed as “BLQ.”
- If all subjects have concentration data values of BLQ for a given time point, all order statistics (minimum, Q1, median, Q3, and maximum) will be displayed as “BLQ.”

3.8. Analysis Visit Windows

3.8.1. Definition of Key Dates and Study Day

Study Day 1 is defined as the day when the first dose of study drug was taken, as recorded on the Study Drug Administration eCRF. For subjects in Treatment Groups 1-3, the earliest of the first dose dates of any component (ie, LEN or F/TAF) is considered as the first dose date of the study drug.

Last Dose Date is defined as follows for subjects who prematurely discontinued study drug according to Study Drug Completion eCRF.

- For subjects who receive SC injection, the last dose date is defined as the latest nonmissing end date of the study drug used with LEN.
- For subjects who do not receive SC injection, the last dose date is defined as the earliest of the last dose date of any study drug.
- If the date of last dose is incomplete or missing (eg, due to lost to follow-up), the latest nonmissing study drug start dates and end dates, the clinic visit dates, and the laboratory visit dates excluding the dates of any follow-up visits will be used to impute the last dose date.

Study Days are calculated relative to Study Day 1 of study drug and derived as follows:

- For postdose study days: Assessment Date – First Dose Date + 1
- For days prior to the first dose: Assessment Date – First Dose Date

Baseline Value is defined as the last value obtained on or prior to the first dose of study drug.

Last Study Date is the latest nonmissing clinic visit dates, and/or the laboratory visit dates, and/or latest AE onset date and end date, whichever is latest, including the any follow-up visit dates, for subjects who prematurely discontinued study according to the Study Completion eCRF.

Last Exposure Date is defined as follows for subjects who prematurely discontinued study drug according to Study Drug Completion eCRF. This date is defined considering the prolonged exposure of LEN after the last dose date of LEN.

- Treatment Groups 1 and 2:
 - For subjects who receive SC injection, last exposure date is defined as last study date.
 - For subjects who do not receive SC injection, last exposure date is defined as the minimum of the last dose date plus 60 days and the last study date.

- Treatment Group 3: last exposure date is defined as the minimum of the last dose date plus 60 days and the last study date.
- Treatment Group 4: last exposure date is defined as the minimum of the last dose date plus 30 days and the last study date.

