8.6. Safety Analysis

For Treatment Groups 1 and 2, all safety data collected on or after the first dose date will be included. For participants who discontinue from the oral GS-6207, only data collected up to 60 days (approximately 5 times the GS-6207 oral dose half-life) after the last dose of the oral GS-6207 will be included. For Treatment Groups 3 and 4, all safety data collected on or after the first dose date and up to 60 days and 30 days, respectively, after the last dose date will be included. All data will be summarized by treatment according to the study drug received. All collected data will be included in data listings.

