7. SAFETY ANALYSES

Safety data will be summarized for subjects in the Safety Analysis Set. All safety data collected up to the last exposure date for subjects who prematurely discontinued study drug or all available data for subjects who were still on study drug will be included in the table summary, unless specified otherwise. All collected data will be included in data listings.

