7.8. Changes From Protocol-Specified Safety Analyses

No change from protocol-specified safety analyses is planned.

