Kruskal-Wallis test for continuous variable (Y):

```
proc npar1way wilcoxon;
  class trt;
  var Y;
run;
```

9) For race and ethnicity, “Not Permitted”, “Missing”, or “Other” will be excluded from percentage calculation and also excluded for p-value generation for categorical data analysis (eg, CMH test or Kruskal-Wallis test).

10) Study Day 1, Last Dose Date and Last Exposure Date

- a) All the key dates were defined in Section 3.8.1.

11) Study Day 1 and Last Dose Date

- a) All the key dates were defined in Section 3.8.1.
- b) Study Day 1 is defined as the earliest of the dose start dates from any Study Drug Administration eCRF (ie, EX, EX_ARV or EX_IV).
- c) Last Dose Date is defined for subjects who prematurely discontinued study drug according to Study Drug Completion eCRF(ie, SDRGCOMP).
 - i) For subjects who receive SC injection(ie, A subject has data in EX_IV.), the last dose date is defined as the latest nonmissing end date of the study drug used with LEN (ie, the last dose date in EX_ARV).
 - ii) For subjects who do not receive SC injection(ie, A subject has no data in EX_IV.), the last dose date is defined as the earliest of the last dose date of any study drug (ie, the earliest of last dose date in EX or EX_ARV).

- d) Study drug administration: Oral reload will be recorded as an “Unscheduled” visit in the Study Drug Administration eCRF. Subjects with oral reload prior to the 1st dose of SC have “Unscheduled” dosing visits occurred prior to Day 15 visit. Subjects who received a total of 5 tablets of LEN (300 mg) (ie, 2 x 300 mg LEN tablets each for the first 2 days and 1 x 300 mg LEN tablet on the 8th day) prior to “Unscheduled” dosing visits followed by Day 15 visit will be classified as oral reload due to missing scheduled SC dosing. Otherwise, subjects will be classified as oral reload due to missing scheduled oral dosing visit.

12) Adherence to QD Study Drug(s)

- a) Adherence based on 1 study drug(Treatment Groups 1, 2, and 4):

$$\begin{aligned} \text{Adherence (\%)} &= 100 \times \frac{\text{Total No. of pills taken}}{\text{Total No. of pills prescribed}} \\ &= 100 \times \frac{\sum \text{No. of pills taken at each dispensing period for each study drug}^{[1]}}{\sum \text{No. of pills prescribed at each dispensing period for each study drug}^{[2]}} \end{aligned}$$

- b) Adherence based on 2 study drugs(Treatment Group 3):

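### For participants never injected, the 60-day safety window runs from the earliest component stop, so it closes early whenever F/TAF stops before oral lenacapavir

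*SAP*

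**What the plan says.** SAP 3.8.1 defines the last dose date for participants recorded on the Study Drug Completion eCRF as having stopped prematurely. For those with no SC injection, "the last dose date is defined as the earliest of the last dose date of any study drug". Appendix 3 item 11(c)(ii) gives the same rule for programming: "the earliest of last dose date in EX or EX_ARV".

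The last exposure date is then built on that date:

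- "Treatment Group 3: last exposure date is defined as the minimum of the last dose date plus 60 days and the last study date".
- In Groups 1 and 2: "For subjects who do not receive SC injection, last exposure date is defined as the minimum of the last dose date plus 60 days", again capped at the last study date.

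The SAP gives the reason for having this second date: "This date is defined considering the prolonged exposure of LEN after the last dose date of LEN". It governs the safety tables, which take "All safety data collected up to the last exposure date for subjects who prematurely discontinued study drug". It also bounds duration of exposure (SAP 4.2.1), treatment-emergent adverse events (7.1.5.1), laboratory summaries and abnormalities (7.2, 7.2.2.1) and concomitant medications (7.4.2).

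For Groups 1 and 2 participants who stop oral lenacapavir, Protocol 8.6 admits "only data collected up to 60 days (approximately 5 times the GS-6207 oral dose half-life) after the last dose of the oral GS-6207", and 8.6.2 applies the same limit to treatment-emergent events. For Group 3, both sections allow 60 days after the last dose date without naming a component. SAP 7.8 states: "No change from protocol-specified safety analyses is planned".

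**The concern.** One date does two jobs that pull in opposite directions. An early stop date is cautious for deciding which HIV-1 RNA values count as on treatment (SAP 6.1.1). The same early date is not cautious for safety, because it ends follow-up sooner. The 60 days stand for about five lenacapavir half-lives, so they serve their purpose only when counted from the last lenacapavir dose. Group 3 takes lenacapavir and F/TAF as two separate products, and SAP 4.2.2.2 works with a discontinuation date for each drug, so separate stop dates are possible.

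The rule is also out of line with the rest of SAP 3.8.1. There, treatment starts at the earliest first dose of any component, and for injected participants the last dose date is the latest end date of the companion drug.

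What is at stake is events and laboratory changes in the weeks after the last lenacapavir dose. These data would exist: under Protocol 6.4.1.2, a Group 3 participant who stops before Week 64 is asked to keep attending through Week 80, or otherwise to complete 30-day and 90-day follow-up.

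**Working it through.** **Inputs.** Oral lenacapavir half-life about 12 days (Protocol 1.2.2.1; the tablet medians in Table 1-4 are 11.0 and 13.4 days). Window of 60 days (Protocol 8.6, SAP 3.8.1). Group 3 premature discontinuations: 4 of 52. Groups 1 and 2: 105 treated, 103 of whom received SC lenacapavir (all Protocol 1.2.2.8).

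**The plan's own figure.** 5 × 12 = 60 days, so the stated five half-lives reproduce. With 11.0 to 13.4 days the product is 55 to 67 days.

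**The date rule.** Let g = last lenacapavir dose date − last F/TAF dose date. The last dose date is the earlier of the two. Measured from the last lenacapavir dose, the cut-off is therefore

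60 − max(g, 0) days,

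subject to the cap at the last study date. Half-lives covered = (60 − g)/12, and the fraction remaining at the cut-off = 0.5^((60 − g)/12), assuming simple first-order decline.

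| g (days) | Cut-off relative to last lenacapavir dose | Half-lives covered | Fraction remaining |
|---|---|---|---|
| 0 or less | +60 | 5.0 | 3% |
| 1 | +59 | 4.9 | 3% |
| 7 | +53 | 4.4 | 5% |
| 30 | +30 | 2.5 | 18% |
| 60 | 0 | 0 | 100% |
| 61 | −1 | none | on drug |

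If lenacapavir stops first or on the same day, nothing in its 60-day window is lost. For g from 1 to 60, the last g days of the window are lost. Only when g exceeds 60 does the cut-off fall before the last lenacapavir dose.

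**Groups 1 and 2 without injection.** Lenacapavir is scheduled on Days 1, 2 and 8, with F/TAF daily from Day 1. The widest gap on scheduled doses is F/TAF last taken on Day 1 and lenacapavir on Day 8: g = 8 − 1 = 7, cut-off +53 days. More usually lenacapavir is the earlier stop, and the SAP then agrees with Protocol 8.6.

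**How many participants.** Never injected: 105 − 103 = 2, assumed to have discontinued prematurely. Ceiling: 4 + 2 = 6, and 6/157 = 3.8% of lenacapavir participants. The documents give g for none of them.

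**The case against.** The strongest reply is that the rule will rarely bite. It applies only to participants recorded as stopping prematurely, not to Group 3 as a whole, and only if F/TAF stops first. Of the four Group 3 stops, three were losses to follow-up and one was a participant decision. Where a last dose date is missing or incomplete, as with loss to follow-up, SAP 3.8.1 imputes it from the latest available drug, visit and laboratory dates, and the cap at the last study date leaves little to lose. All of this stands, and it keeps the point small.

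Several exceptions also stand. Adverse events leading to discontinuation always count as treatment-emergent (SAP 7.1.5.1). All deaths enter the high-level summary (7.1.6.1). An event with both dates completely missing counts as treatment-emergent (7.1.5.2). All collected data are listed (SAP 7). What is lost is lost from summary tables, not from the record.

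Three stronger readings are tempting, and the documents do not support them:

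- That events are dropped while lenacapavir is still being taken. This needs more than 60 days of lenacapavir after F/TAF has ended. No section describes such use, and Protocol 5.3 has Group 3 take the two together.
- That the loss is concentrated in participants who stop because of toxicity. None of the four Group 3 stops was for an adverse event.
- That the SAP contradicts the protocol in every group. The protocol sections tied to the last oral lenacapavir dose concern Groups 1 and 2. For Group 3 the protocol names no component, so there the SAP resolves an ambiguity, though in a way that conflicts with its own stated purpose.

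**Conclusion.** The rule is wrong as written. It appears in both the SAP text and the programming specification, and nothing overrides it. Relative to 60 days after the last lenacapavir dose, it can only shorten follow-up, never lengthen it. It conflicts with the SAP's own purpose for the last exposure date and, when F/TAF stops first in Groups 1 and 2, with Protocol 8.6 and 8.6.2. SAP 7.8 declares no such change.

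The expected effect is small. The ceiling at the Week 54 cut is 4 of 52 in Group 3, plus 2 oral-only participants in Groups 1 and 2 whose gap is about 7 days at most on scheduled doses. The true number may be lower or zero. The day-loss figures show how the rule behaves and do not estimate what was lost.

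This rests on three assumptions: a 12-day half-life; that the two participants never injected did discontinue; and that Protocol 8.6 read the same in amendment 3, on which the SAP says it is based. The protocol available here is a later text, since it reports Week 54 results. The conflict with the SAP's own stated purpose does not depend on that last assumption.

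**What to change.** Keep the earliest-stop date for the on-treatment HIV-1 RNA rule in SAP 6.1.1. Neither document says why the earliest date was chosen, but it is defensible there. For participants without an SC injection, define the last exposure date separately:

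- Groups 1 and 2: last oral lenacapavir dose plus 60 days, which matches Protocol 8.6. Using the latest component here would itself depart from the protocol, because continued F/TAF would carry the window past the protocol's limit.
- Group 3: latest last dose of either component plus 60 days. This also covers F/TAF continuing after lenacapavir.

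Cap each at the last study date, as now. Amend SAP 3.8.1 and Appendix 3 item 11, and state the Group 3 anchor in SAP 7.8. Because the SAP is final, its section 1 requires a later change to be documented in the clinical study report. The cost is one derived variable, a few sentences and a rerun of the affected safety tables. Reporting each component's stop date for the participants concerned (six at most) would show whether any result changes.
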